## 2. INTRODUCTION

Topical Remedy, LLC. is developing Merlin, a novel topical formulation that can be used to treat viral infections of the skin. It is composed of two commonly used compounds, glycolic acid (0.6%) and ethanol (10%), each with known safety and side effect profiles. This product, intended for over-the-counter distribution, will consist of single treatment foam applicators pre-filled with the Merlin solution.

Approximately 20 to 40% of the adult population experience recurrent outbreaks of herpes labialis, or cold sores. In almost all cases, the disease is due to reactivation of chronic, latent herpes simplex virus type 1 infection from the ganglion of the trigeminal nerve. When the latent infection is activated by any one of a variety of triggers, virions descend through the sensory nerve axons and reinfect the peripheral epithelium. The new herpes labialis lesion matures within 8 hours after onset, leaving very little time for successful chemotherapeutic intervention.

The current standard of care for recurrent herpes labialis involves an oral or topical antiviral given episodically at the onset of each recurrence. A variety of topical over-the-counter preparations are available, but in most cases the mechanism of action is ambiguous and very few clinical trials have been performed to define their efficacy. Studies of acyclovir ointment have provided little evidence of efficacy for herpes labialis in immunocompetent subjects. Acyclovir and penciclovir cream-based formulation are both approved for treatment of herpes labialis, but while both do penetrate the skin more effectively than the acyclovir ointment, both exhibit relatively limited efficacy with regard to shortening the duration of a herpetic episode. Docosanol 10% cream (Abreva; GlaxoSmithKline) is the most well-studied over-the-counter product, with 2 randomized trials suggesting some efficacy of treatment. However, because an unrelated placebo was used in these studies, the true level of efficacy cannot be objectively determined. All these approved topical treatments, as well as Valtrex and Famvir, the approved oral treatments, provide, at best, approximately a one day shortening of the duration of a herpetic episode, and none of them results in a reduction in the percent of the worst outbreaks, the so-called classical lesions. Even the most recently approved new treatment, Xerese, a combination of acyclovir and hydrocortisone, provides less than one day shortening of the herpetic episode, and an only slightly better, 1.5 day, decrease in the time until complete healing of the outbreak. Xerese does claim to significantly reduce the percent of classical lesion outbreaks, but the increase in the percent of so-called “aborted lesions” with Xerese is only modestly better than the essentially ineffective acyclovir cream (42% for Xerese versus 35% for acyclovir cream).

A pilot clinical study (Protocol TR-H-111) was performed by the sponsor to investigate the potential skin irritancy of Merlin. The study involved the application in 40 subjects, of a total of thirty-six (36) treatments over four (4) days. More specifically, each subject administered three (3) applications of Merlin or placebo, depending on how a subject was randomized, twenty (20) minutes apart, for each set of treatments. These sets of treatments were repeated two (2) more times at six (6) and twelve (12) hour after the start of the initial treatments, for a total of nine (9) treatments of active or placebo on Day 1. The sets of treatments were then re-applied three (3) times each day for three (3)

additional days, resulting in the above noted total of four (4) days of treatment with thirty-six (36) applications of active or placebo.

On Day 1, scoring of the skin reaction was performed at the treatment site within 5 min prior to each initial application in a set of 3 applications, and within 5 minutes after the third application in the set of 3 applications. On Days 2 through 4, scoring of the treatment site was performed only for the first set of applications, when the subject was in the clinic for the first set of test article applications. Similarly to the timing for the evaluations on Day 1, scoring of the skin reaction in the treatment site was performed within 5 min prior to the initial application in the first set of 3 applications, and within 5 minutes after the third application in the first set of 3 applications. Skin reaction scoring on Day 5 was performed at 24 hours ( $\pm$  1 hour) from the time of the first treatment on Day 4. Any skin reactions noted on Day 5 were to be followed either with daily clinic visits or telephone contacts, as deemed appropriate, until the event was resolved.

The results of the skin irritation portion of the study revealed that all treatments were very well tolerated by all subjects, with no significant skin irritation and only a few, mild adverse events. Minimal erythema was the most notable reaction observed immediately after treatment in three subjects, and this resolved in all subjects within 1 hour. The only other reported adverse drug related adverse event was mild burning on treatment application in one subject; this also resolved rapidly.

Merlin, therefore, appears to be safe as the only reported adverse events were very mild skin irritation in three subjects and mild burning on application in one subject.

This was followed by Phase 2 study (TR-H-211) the primary objective of which was to assess the efficacy of Merlin as compared to a placebo treatment, on the clinician assessed duration to complete healing of the herpetic episode. Other endpoints included the clinician assessed: 1) prevention of progression to a classical lesion associated with herpes labialis; 2) duration of classical herpetic lesions; and 3) duration of the herpetic episode. The safety of Merlin was also evaluated.

A total of 469 subjects were enrolled in the study with 172 subjects actually treated. After being enrolled and randomized into the study, subjects were sent home with a kit containing a bottle filled with either Merlin (active) or the 10% ethanol placebo solution and a packet of foam-tipped applicators sufficient to apply three study treatments (nine (9) applications). The subject was instructed to contact the clinic by telephone at the first signs and/or symptoms of a recurrent herpetic episode (Stage 0 or 1, prodromal or erythema). The lesion then was confirmed by telephone interview with the subject, and upon confirmation of the lesion, the subject was instructed to begin treatment immediately, thereby initiating the Treatment Phase of the study. The subject was told to continue treatment for the remainder of the day with the treatment schedule as described above for the Phase 1 study, and to continue to treat with a set of three (3) treatments, three times each day, for a total of twelve (12) sets of treatments resulting in thirty-six (36) applications in total. The subject also was instructed to return to the clinic within 24 hours of the initial treatment for evaluation of the stage of the herpetic lesion.

Subjects reported daily for a minimum of 3 consecutive days, with the last clinic visit at the time of complete healing (Stage 7 - normal skin) or at 14 days, whichever is earlier. Subjects will be contacted by phone, for a safety assessment, 2 weeks after they complete the Treatment Phase of the study.

The results of this study found that twelve (12) treatments with Merlin solution, administered 6 hours apart (up to 3 per day) over 96 hours, was generally safe and tolerable in the treatment of subjects with lesions associated with herpes simplex labialis. The majority of treatment-related AEs were classified as mild in intensity. No treatment related AEs in any cohort were classified as severe.

An a priori analysis found that those subjects, who treated with Merlin at first visible signs of a herpetic lesion, erythema, rather than immediately at first symptoms of a herpetic lesion, the prodromal stage, exhibited statistically significant efficacy as compared to placebo for the duration of the classical lesion. The same a priori analysis found trends towards significance for the endpoints of complete healing, duration of the herpetic episode, cumulative lesion size, duration of the hard scab, and the subject assessed severity of lesion pain.

This current clinical study is a follow-up Phase 2 trial using the same Merlin formulation as was used in the studies described above. This trial, as the previous Phase 2 study, will have two treatment arms comparing the safety and efficacy of Merlin solution to that of a placebo (10% ethanol) with treatment at first visible signs of a herpetic episode.

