**Methodology (cont.):**

After being enrolled and randomized into the study, subjects will be sent home with a kit containing a bottle filled with either Merlin (active) or the 10% ethanol placebo solution and a packet of foam-tipped applicators sufficient to apply three (3) study treatments (nine (9) applications). The subject will be instructed to contact the clinic by telephone at the first signs and/or symptoms of a recurrent herpetic episode (Stage 0, prodrome, Stage 1, erythema, or Stage 2, papule/edema). The lesion and lesion stage then will be confirmed by telephone interview with the subject. Subjects reporting either a Stage 1 or Stage 2 lesion will be instructed to begin treatment immediately, thereby initiating the Treatment Phase of the study. Subjects reporting only Stage 0 symptoms, i.e. no visible signs of a cold sore lesion, will be instructed to monitor their lesion and to call the clinic immediately upon observing any early visible signs of a cold sore, i.e. redness or swelling, representing a Stage 1 or Stage 2 lesion. Once the subject calls in and confirms by telephone interview that their lesion has reached Stage 1 or 2, they will be instructed to begin treatment immediately. The subject will be told to continue treatment for the remainder of the day with the treatment schedule outlined above, and to continue to treat with a set of three (3) applications, three (3) times each day, for a total of twelve (12) treatments resulting in thirty-six (36) applications in total. The subject also will be instructed to return to the clinic within 24 hours of the initial treatment for evaluation of the stage of the herpetic lesion.

Subjects will report daily for a minimum of 3 consecutive days, with the last clinic visit at the time of complete healing (Stage 7 - normal skin) or at 14 days, whichever is earlier. Subjects will be contacted by phone, for a safety assessment, 2 weeks after they complete the Treatment Phase of the study.

**Number of Subjects:** Approximately four hundred and fifty (450) subjects will be enrolled into the study, 225 into the active treatment group and 225 into the placebo treatment group. At least 75 subjects in the active treatment group, and 75 subjects in the placebo treatment group, will enter the Treatment Phase of the study and administer treatments.

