### **5.2.1 Inclusion Criteria**

1. Male or female subject 18-75 years of age
2. Female subjects must be using a medically acceptable form of birth control during the study. Acceptable birth control measures include, but are not limited to: abstinence, oral contraceptive pills or patch, injectable contraception, barrier contraceptives (condom, diaphragm with spermicide), IUD, vaginal contraceptive ring, surgical (hysterectomy, tubal ligation), vasectomized partner, and natural post-menopausal inability to conceive. Menopause is defined for this protocol as starting one year after the time of the last menstrual period.
3. Subject must have a history of recurrent herpes labialis and report at least 3 separate recurrences (i.e. multiple herpetic lesions in one outbreak count as only one episode) during the preceding 12 months.
4. Subject must have a history of experiencing prodromal symptoms of cold sores (e.g. itching, tingling, or burning) during at least half of their previous cold sore episodes.
5. Subject must have a history of at least half of their cold sore episodes producing classical lesions (i.e., episodes that progressed through macule, papule, vesicle, crust, and healed).
6. Subject must provide voluntary written informed consent to participate in this study.

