## **10.4 General Methodology**

All statistical tests will be done using two-sided tests and a Type I error rate of 0.05.

Data listings will be based on all subjects in the safety population.

Continuous variables will be summarized using descriptive statistics, specifically the mean, median, standard deviation, minimum and maximum values. Categorical variables will be summarized by frequencies and percentages.

The primary analyses will compare the active treatment arm to the placebo control arm. Aside from any placebo effect, there should be no efficacy associated with the placebo solution. As a secondary analysis, all statistical comparisons will be performed with the treated subjects stratified based on whether they treated at erythema (Stage 1) or papule/edema (Stage 2).

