#### **10.7.9 Sample Size Determination**

The sample size for this study was based upon the results of the previous Phase 2 study, TR-H-211. In that study, Merlin demonstrated a statistically significant ( $p=0.0276$ ) effect on the duration of classical lesion endpoint for subjects beginning treatment at Stage 1 (erythema) with only 32 subjects treated with Merlin and 22 placebo subjects. Clinical investigations with Famvir and other independent studies, that initiate treatment within hours of the onset of prodromal symptoms (Stage 0) have demonstrated that 1/3 of all subjects enrolled in herpes labialis studies will have spontaneously aborted lesion. Any calculation of clinical trial size, therefore, must consider that factor. When, however, treatment is initiated at the erythema stage (Stage 1), as in the Merlin Phase 2a (TR-H-211) study, the incidence of spontaneously aborted lesions declines to 25%. As a result, a larger percentage of subjects will demonstrate classical lesions in Merlin studies than was seen in the Famvir, or similar previous studies. This was factored in when performing

power calculations for this Phase 2b clinical study. Those calculations determined that 144 subjects would provide a 95% likelihood of statistical significance for the herpetic episode endpoint. Merlin decreased the duration of herpetic episode in subjects that began treatment at stage 1 by 41 hours, with a p-value of 0.055 in the Phase 2a study. The herpetic episode endpoint includes the subjects with aborted lesions.

As a result, a 150 subject clinical trial will have approximately 60 subjects progress to classical lesions in each treatment arm and we can be highly confident of having the power to demonstrate a highly significant difference for the duration of classical lesion endpoint, as shown in the Phase 2a results. In addition, a 150 subject clinical trial should have greater than 95% likelihood of demonstrating a statistically significant Merlin effect on herpetic episode as a secondary endpoint.

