### 3 Sample Size

The sample size for this study was based upon the results of the previous Phase 2 study, TR-H-211. In that study, Merlin demonstrated a statistically significant ( $p=0.0276$ ) effect on the duration of classical lesion endpoint for subjects beginning treatment at Stage 1 (erythema) with only 32 subjects treated with Merlin and 22 placebo subjects. Clinical investigations with Famvir and other independent studies, that initiate treatment within hours of the onset of prodromal symptoms (Stage 0) have demonstrated that 1/3 of all subjects enrolled in herpes labialis studies will have spontaneously aborted lesion. Any calculation of clinical trial size, therefore, must consider that factor. When, however, treatment is initiated at the erythema stage (Stage 1), as in the Merlin Phase 2a (TR-H-211) study, the incidence of spontaneously aborted lesions declines to 25%. As a result, a larger percentage of subjects will demonstrate classical lesions in Merlin studies than was seen in the Famvir, or similar previous studies. This was factored in when performing power calculations for this Phase 2b clinical study. Those calculations determined that 144 subjects would provide a 95% likelihood of statistical significance for the herpetic episode endpoint. Merlin decreased the duration of herpetic episode in subjects that began treatment at stage 1 by 41 hours, with a p-value of 0.055 in the Phase 2a study. The herpetic episode endpoint includes the subjects with aborted lesions.

As a result, a 150 subject clinical trial will have approximately 60 subjects progress to classical lesions in each treatment group and we can be very confident of having the power to demonstrate a highly significant difference for the duration of classical lesion endpoint, as shown in the Phase 2a results. In addition, a 150 subject clinical trial should have greater than 95% likelihood of demonstrating a statistically significant Merlin effect on herpetic episode as a secondary endpoint.

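### The planning effect comes from subjects who first called at erythema, so the episode power above 95% is unsupported for a trial that also treats prodrome callers who waited, and it does not reproduce even without them

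*Protocol*

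**What the plan says.** **TR-H-211 (Protocol 2).** Subjects telephoned at Stage 0 or 1 and, "upon confirmation of the lesion, the subject was instructed to begin treatment immediately". Of 469 enrolled, 172 were treated. Efficacy is reported for those who started at erythema: "An a priori analysis found that those subjects, who treated with Merlin at first visible signs of a herpetic lesion, erythema, rather than immediately" at prodrome, had a significant benefit over placebo on classical lesion duration. No effect is given for those who started at prodrome.

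**Sample size (Protocol 10.7.9, SAP 3).** The basis is the Stage 1 starters, "with only 32 subjects treated with Merlin and 22 placebo subjects": p=0.0276 for classical lesion duration, and 41 h with p=0.055 for the herpetic episode. From this, 144 subjects are said to give 95% for the episode endpoint, and "a 150 subject clinical trial should have greater than 95% likelihood of demonstrating a statistically significant Merlin effect on herpetic episode as a secondary endpoint". No numerical power is given for the primary endpoint.

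**This trial (Synopsis, Protocol 4 and 7.2.1).** "Subjects reporting only Stage 0 symptoms, i.e. no visible signs of a cold sore lesion, will be instructed to monitor their lesion" and to call again once redness or swelling appears; only then may they treat. Sites re-contact them every 6 to 18 hours. Stage 2 starters are also admitted. Enrolment criterion 4 (Protocol 5.2.1) reads: "Subject must have a history of experiencing prodromal symptoms of cold sores (e.g. itching, tingling, or burning) during at least half of their previous" episodes.

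**Analysis (Protocol 10.4; SAP 7.2, 7.13, 7.13.5).** Comparisons are made overall and by stage at treatment start (Stage 1 or 2). Neither document names stage at first call as an item to be recorded or analysed.

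**The concern.** In TR-H-211, stage at treatment start and stage at first call were the same thing. Here they are not. Someone who starts at erythema may have called for the first time at erythema, or may have called at prodrome and been held. Only the first kind supplied the planning effect, yet 10.7.9 and SAP 3 apply that effect to all 150 treated subjects.

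The Introduction says lesions mature within 8 hours of onset and leave little time for intervention. That is a reason to state, rather than silently assume, that the two kinds of starter respond alike. The point holds even if everyone starts at Stage 1, so it is separate from the admission of Stage 2 starters, and the planned Stage 1 versus Stage 2 split mixes the two kinds within Stage 1.

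At stake are the credibility of the power statement and the ability to describe results in prodrome callers at all. If first-call stage is not captured at the time, it may not be recoverable later.

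**Working it through.** **1. Reproducing the stated 95% with no dilution.** Inputs from Protocol 10.7.9: 41 h, p=0.055, n=32 and 22. Protocol 10.4: "All statistical tests will be done using two-sided tests and a Type I error rate of 0.05". The SD is not printed, so it is solved from the p-value, treating it as a two-sample t-test with equal SDs.

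- SE = 41 / 1.963 (t, 52 df) = 20.9 h.
- SD = 20.9 / sqrt(1/32 + 1/22) = 20.9 / 0.277 = 75.4 h.
- 72 per arm: SE = 75.4 × sqrt(2/72) = 12.6 h; 41/12.6 = 3.26; power about 90%.
- 75 per arm: SE = 12.3 h; 41/12.3 = 3.33; power about 91%.
- 95% needs about 178 subjects at this SD. With 144 subjects it needs an SD near 68 h.
- A one-sided 0.05 test comes close (about 95% at 144), but that contradicts Protocol 10.4.

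**2. Classical-only reading of the 54.** The 32+22 are quoted beside the classical-lesion p-value, so they may exclude aborted lesions. With 25% aborted (10.7.9), Stage 1 starters would number 54/0.75 = 72, about 43 and 29. Then SE = 41/1.951 = 21.0 h, SD = 21.0/0.240 = 87.4 h, and power at 75 per arm is about 81%.

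**3. Share of treated subjects who waited.** Not stated; extrapolated from TR-H-211.

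- Not Stage 1 starters: 172 − 54 = 118 (69%), or 172 − 72 = 100 (58%).
- Prodromes that never become visible, from the plan's one third versus 25% aborted: (1/3 − 0.25)/0.75 = 11%. Waiters are then 104.9/(54 + 104.9) = 66%, or 88.9/(72 + 88.9) = 55%.
- Further losses (lesions already past Stage 2 at call-back) and first callers at Stage 2 lower the share. It falls below half if more than 1 − 54/118 = 54%, or 1 − 72/100 = 28%, of prodrome callers are lost. With 55% lost and 40 Stage 2 first callers per 172, it is 45/(45 + 72 + 40) = 29%.
- Range over the scenarios tried: about 29% to 69%.

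**4. Sensitivity, not estimate.** Mean effect = 41 × (1 − f + f·r), where f is the share waiting and r their relative effect. The documents give no value for r. At r = 1 power stays at 91% (81% with SD 87 h). At an assumed r = 0.5, with 75 per arm:

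- f = 29%: 35.1 h; 81% (SD 75), 68% (SD 87)
- f = 42%: 32.4 h; 74%, 62%
- f = 55%: 29.7 h; 67%, 54%
- f = 66%: 27.5 h; 60%, 48%

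**5. Precision of a split by first-call stage.** With SD 75.4 h and 55% waiting (41.25 and 33.75 per arm), the SE of the difference between stratum effects is 75.4 × sqrt(2/41.25 + 2/33.75) = 24.8 h, a 95% interval of about ±49 h. At 66% it is about ±51 h. Either half-width exceeds the whole 41 h effect.

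**The case against.** The best defence is that the objective is Merlin against placebo in subjects treating at first visible signs (Protocol 3 and 4), and randomisation protects that comparison whatever the mix of callers. This stands in full.

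Second, the effect in waiting subjects may be no smaller. They are alerted and monitored, and might start earlier within erythema. The TR-H-211 erythema starters may themselves have included people who had a prodrome but called only at redness. The documents do not settle either point, so the reduced-power figures in step 4 rest on an assumed r.

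Third, the added split is too imprecise to separate full effect from none in waiters, and would not by itself explain a null result. This also stands, and is why the split should be descriptive only.

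A reader might infer more than the documents support:

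- That waiters will be the majority. No share is stated, and the extrapolation falls on either side of half.
- That the TR-H-211 erythema starters chose to delay or were self-selected. They may have had no prodrome or not noticed it; only the stage at which they called is known.
- That waiting has been shown to cost power. The gap from above 95% to 91% comes from step 1 and has nothing to do with waiting.
- That the trial should show whether waiting is better than treating at prodrome. There is no immediate-treatment arm, so no analysis here could do so.

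The defence does not answer two things: the stated power fails on the plan's own inputs, and its transfer to held-back prodrome callers is neither stated nor examinable in the planned analyses.

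**Conclusion.** The point holds as a fault in the power statement and a gap in what is recorded and described, not as a threat to the validity of the main comparison. Episode power at 75 per arm is about 91%, or about 81% on the classical-only reading, rather than above 95%. Even these figures require the full TR-H-211 effect in subjects who called at prodrome and waited, perhaps 30% to 70% of those treated. At half effect in 29% to 66% of subjects, power would run from about 81% down to 60% with SD 75 h. That is an assumed scenario, not a forecast.

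The figures rest on a t-test reading of p=0.055, equal SDs, normality and a two-sided 0.05 level. The Wilcoxon test would lower them by about one point under normality. They concern the secondary episode endpoint; the primary endpoint carries the same unstated transfer assumption but no numerical power to correct.

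**What to change.** 1. **Protocol 10.7.9 and SAP 3.** Replace the claim of more than 95% with about 91% (about 81% if the 54 were classical lesions only). State which reading of the 54 is correct, and the SD and test used. Say that the figure assumes the full effect seen in TR-H-211 erythema callers also applies to prodrome callers who waited. Add the step 4 range, labelled as assumed.
2. **CRF.** Record stage at first call and time from first call to first treatment for the treated episode. Sites already learn both through the calls in Protocol 7.2.1.
3. **SAP 7.13.** Add a descriptive Hodges-Lehmann estimate with 95% CI for the primary and episode durations by first-call stage (Stage 0 versus visible). Note that the between-stratum comparison is imprecise (about ±50 h) and does not test waiting against immediate treatment.

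The primary rank test needs no change, and nothing here calls for a change to the waiting rule. The cost is two CRF items, one table and some wording. The downside is a less favourable power statement and one imprecise descriptive subgroup.
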